3.4.4.4 Pregnancy Testing

In females of child-bearing potential (FCBP) urine and serum β -HCG will be performed weekly for the first 28 days of study participation and then every 28 days while on study, at study drug discontinuation, and at day 28 following study drug discontinuation. If menstrual cycles are irregular, the pregnancy testing must occur weekly for the first 28 days and then every 14 days while on study, at study discontinuation, and at days 14 and 28 following study drug discontinuation.

- 3.4.4.5 Correlative Studies (see section **5.1.2**)
- 3.4.4.6 Response evaluation (see sections **6.2.1** and **6.2.2**)

3.4.5 Post-treatment Evaluation

Subjects will be reviewed at day 29 of their final cycle, and further evaluated for short term toxicity a further 28 days (± 7 days) after completion of the final cycle. Objective signs, relevant positive and negative findings on history and examination, and clinical toxicities will be

evaluated and recorded each visit. If any drug toxicity remains at the follow-up evaluation, subjects will be followed as medically indicated until the toxicity stabilizes or resolves.

3.4.5.1 Clinical Examination

3.4.5.2 Clinical Laboratory Data

- 3.4.5.2.1 CBC with differential and reticulocyte count
- 3.4.5.2.2 Acute care panel (Sodium, Potassium, Chloride, CO₂, Creatinine, Glucose, and Urea Nitrogen)
- 3.4.5.2.3 Mineral panel (Phosphorus, Magnesium, Albumin, and Calcium)
- 3.4.5.2.4 Hepatic panel (Alkaline Phosphatase, ALT, AST, Total Bilirubin, and Direct Bilirubin)
- 3.4.5.2.5 C-reactive protein
- 3.4.5.2.6 Creatine kinase, uric acid, LDH, amylase and lipase
- 3.4.5.2.7 Thyroid stimulating hormone (TSH)
- 3.4.5.2.8 APTT, PT, thrombin time (TT), fibrinogen, D Dimer
- 3.4.5.2.9 HIV viral load if HIV infected
- 3.4.5.2.10 Lymphocyte phenotype TBNK (requires simultaneous CBC and automated differential)
- 3.4.5.2.11 EBV viral load if seropositive
- 3.4.5.2.12 CMV viral load if seropositive
- 3.4.5.2.13 HBV viral load if evidence of past or current infection
- 3.4.5.2.14 HCV viral load if evidence of past or current infection.

3.4.5.3 Pregnancy Testing

In females of child-bearing potential (FCBP) urine and serum β-HCG will be performed at study drug discontinuation, and at day 28 following study drug discontinuation. If menstrual cycles are irregular, the pregnancy testing must occur at study drug discontinuation, and at days 14 and 28 following study drug discontinuation.

3.4.5.4 Correlative Studies (see section [5.1.2](#))

3.4.5.5 Response Evaluation (see sections [6.2.1](#) and [6.2.2](#))

3.4.5.6 Long-term follow up

Subjects will be clinically evaluated every 3 months for the first 6 months after completion of therapy, then every six months to a total of two years after therapy, and then annually to a total of five years after completion of therapy to evaluate for disease progression and the development of secondary malignancies. CBC, Acute care, mineral and hepatic panels, HIV VL if HIV infected, and Lymphocyte phenotype TBNK will be rechecked or, if performed by primary care in the community, outside results will be reviewed.

For subjects who receive an additional course of pomalidomide, clinical evaluation will be for five years following the completion of the *first* course of therapy including a minimum of two years following the completion of the *second* course of therapy in any case where follow up would otherwise be completed in less than two years after the second course. The visit schedule will be increased as follows to be: every 3 months for the first 6 months after completion of the

second course of therapy, then every six months to a total of two years after the second course of therapy, and then annually to a total of five years after completion of the first course of therapy.

During follow-up visits, KS lesions will be assessed, and if patients have not received additional systemic therapy for KS (except for antiretroviral therapy), disease progression will be assessed. For patients who have received other therapies or have previously progressed, this information as well as the status of their KS lesions will be recorded at the time of the visit (without necessarily assessing disease progression).

The time of the visits may be accelerated or delayed somewhat if need be because of difficulty scheduling, etc. This follow up will be in parallel with primary care provision in the community.

If patients cannot or refuse to come in for follow-up visits, an attempt will be made to obtain data on the patient's general status, their KS treatment, the status of their KS, and secondary malignancies from their primary care providers in the community, and this will not constitute a protocol deviation. For this protocol, "secondary malignancies" will be defined as all new malignancies, whether or not they have been previously reported as associated with pomalidomide. It will include malignancies known to be associated with KSHV or HIV infection.

3.5 COST AND COMPENSATION

3.5.1 *Costs*

NIH does not bill health insurance companies or participants for any research or related clinical care that participants receive at the NIH Clinical Center. If some tests and procedures performed outside the NIH Clinical Center, participants may have to pay for these costs if they are not covered by insurance company. Medicines that are not part of the study treatment will not generally be provided or paid for by the NIH Clinical Center.

3.5.2 *Compensation*

Participants will not be compensated on this study.

3.5.3 *Reimbursement*

The NCI will cover the costs of some expenses associated with protocol participation. Some of these costs may be paid directly by the NIH and some may be reimbursed to the participant/guardian as appropriate. The amount and form of these payments are determined by the NCI Travel and Lodging Reimbursement Policy.

3.6 CRITERIA FOR REMOVAL FROM PROTOCOL THERAPY AND OFF STUDY CRITERIA

Prior to removal from study, effort must be made to have all subjects complete a safety visit approximately 28 days (± 7 days) following the last dose of therapy.

3.6.1 *Off-Therapy*

- 3.6.1.1 Any toxicity which is grade 4 and a dose limiting toxicity as defined in Section [3.1.2](#) at least possibly related to pomalidomide.
- 3.6.1.2 Any toxicity which is grade 3 and a dose limiting toxicity as defined in Section [3.1.2](#) at least possibly related to pomalidomide that does not resolve within 28 days to either grade 1 or the grade the patient had at entry.

- 3.6.1.3 Development of deep venous or arterial thrombosis, whether symptomatic or not, or development of a second on-study superficial venous thrombosis.
- 3.6.1.4 Pregnancy.
- 3.6.1.5 Achievement of pathologically confirmed complete remission.
- 3.6.1.6 Completion of six cycles of therapy (unless continuing to derive clinical benefit, as described in Section 3.1.4, in which case up to 12 cycles may be administered).
- 3.6.1.7 Clinically significant progressive disease compared with the tumor baseline for the current course of therapy by NCI-HAMB modified ACTG KS response criteria, sustained for eight weeks and not attributed to immune reconstitution syndrome. As KS may wax and wane, and improvements may be seen despite an initial period of progression, physician investigators may continue therapy through the first 6 cycles, despite meeting formal criteria for progressive disease, as long as disease progression is not clinically significant. Such cases must be discussed with the Principal Investigator and study subject. Clinically significant progression includes all symptomatic visceral disease and disease which is organ- or life-threatening.
- 3.6.1.8 ECOG performance status ≥ 3 .
- 3.6.1.9 Significant non-adherence to protocol therapy or HAART (the latter only in subjects with HIV-associated KS).
- 3.6.1.10 Inability to achieve HIV viral control, defined as failure to maintain an HIV VL $<10,000$ copies/mL persisting on at least two successive determinations at least four weeks apart and persisting despite optimization of HAART regimen. If a change in HAART regimen is required, a further period of up to eight weeks to assess the effect of this change on HIV VL is allowable.
- 3.6.1.11 Subject requests to be withdrawn from active therapy
- 3.6.1.12 Subjects may be taken off therapy at the discretion of the Principal Investigator

3.6.2 *Off Study Criteria*

- 3.6.2.1 Subjects may be taken off study at the discretion of the Principal Investigator.
- 3.6.2.2 Subjects may withdraw from the study as a matter of personal preference.
- 3.6.2.3 Subject has completed the study follow-up period
- 3.6.2.4 Death

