1.2.1.3 Therapies

In patients with HIV-associated KS, HAART is a cornerstone of management. It appears that HIV infection can promote the development of KS in a variety of ways, including immunosuppression, cytokine dysregulation, and direct effects of HIV in enhancing spindle cell proliferation and KSHV cellular infection(13, 16, 18, 70, 71). Institution of HAART alone can alone lead to KS regression, and may be sufficient therapy in some cases, presumably through its effect on these factors(18, 72, 73). Remissions are most likely to occur in patients who have not previously received antiretroviral therapy, those with effective HIV suppression and associated immune reconstitution, and those who have limited disease(18, 72). Patients with KS who are already receiving effective HAART are much less likely to respond to continued antiretroviral therapy alone(71). Regardless of the extent of KS, HAART improves durability of response and overall survival in patients with HIV-associated KS. Hence, for those patients who do not

respond to HAART alone or who are felt to need additional specific KS therapy, HAART should accompany specific KS therapy.

In patients with symptomatic visceral disease, advanced cutaneous or lymphatic involvement, or disease whose response to HAART is unsatisfactory, additional systemic therapy with cytotoxic agents is indicated. First line cytotoxic therapy in the United States generally comprises liposomal doxorubicin (as the liposomal preparation likely improves delivery to the lesions), based on phase III studies with liposomal preparations of doxorubicin and daunorubicin conducted prior to widespread availability of HAART. These demonstrated overall response rates of approximately 46-75%, superior to those seen with combination chemotherapy, and good tolerability([74-81](#)). Paclitaxel is also FDA-labeled for use in KS, based on phase II studies conducted by HAMB investigators and others([82-84](#)). In a recently-published multicenter study comparing liposomal doxorubicin with paclitaxel conducted by the AIDS Malignancy Consortium, overall response rates were similar for each agent (46% versus 56%, respectively)[\(85\)](#). However, the paclitaxel arm was characterized by somewhat hematologic and gastrointestinal toxicity and a higher proportion of patients failing to complete therapy.

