- 2.1.1.10 Females of childbearing potential (FCBP) as defined in **Appendix 1** must have a negative serum or urine pregnancy test with a sensitivity of at least 25 mIU/mL within 14 days prior to and again within 24 hours before starting pomalidomide and must either commit to continued abstinence from heterosexual intercourse or begin TWO acceptable methods of birth control, one highly effective method and one additional effective method AT THE SAME TIME, at least 28 days before she starts taking pomalidomide. FCBP must also agree to ongoing pregnancy testing. Men must agree to use a latex condom during sexual contact with a FCBP even if they have had a vasectomy. All subjects must be counseled at a minimum of every 28 days about pregnancy precautions and risks of fetal exposure. See Section **16.1 Appendix 1**, Risks of Fetal Exposure, Pregnancy Testing Guidelines and Acceptable Birth Control Methods, and also Section **16.2, Appendix 2: Pomalidomide Education and Counseling Guidance Document**.
- 2.1.1.11 All study participants must agree to be registered into the mandatory POMALYST REMSTTM program, and be willing and able to comply with the requirements of the POMALYST REMSTTM program.
- 2.1.1.12 Females of reproductive potential must be willing to adhere to the scheduled pregnancy testing as required in the POMALYST REMSTTM program.
- 2.1.1.13 Able to take aspirin 81mg daily or if intolerant of aspirin, able to take a substitute thromboprophylaxis such as low molecular weight heparin at a thromboprophylactic dose (such as enoxaparin 0.5mg/kg once daily).
- 2.1.1.14 Willing and able to give informed consent.
- 2.1.1.15 For subjects with HIV-associated entered after a tolerable dose has been determined, KS lesions must be either:
 - 2.1.1.15.1 Increasing despite HAART and HIV suppression below the limit of detection (48 copies/mL) in the two months prior to screening *or*
 - 2.1.1.15.2 Stable despite HAART for at least three months. Stable disease must be symptomatic (examples of symptomatic disease include disease associated with pain, edema, psychological distress and/or social withdrawal).

This is to gain preliminary information about pomalidomide activity without confounding due to HAART initiation.

2.1.2 **Exclusion Criteria**

- 2.1.2.1 Symptomatic pulmonary KS.
- 2.1.2.2 Symptomatic visceral KS (except for non-ulcerating disease restricted to the oral cavity).

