- Subjects who otherwise meet the criteria for a CR but still have residual tumor-associated edema or effusions will be classified as having a PR.

Progressive Disease

- For those criteria that involve measurement of lesions in the clinic, the designation of progression should be made, when feasible, only when the criteria below have been met in two measurements spaced at least 1 week apart. For the assignment of progressive disease for the primary outcome analysis, progression will be defined in comparison to baseline measurements.
- An increase of 25% or more over baseline in the number of lesions and/or the size (sum of the products of the largest perpendicular diameters) of the marker lesions *or*
- A change in character from macular to plaque-like or nodular of at least 25% of the lesions *or*
- New visceral sites of involvement or progression of visceral disease *or*
- The development of new or increasing tumor-associated edema or effusion that lasts at least 1 week and interferes with the patient's normal activities.
- Clarification: There is a certain variability in the measurement of KS lesions, and this becomes particularly problematic if patients have very few lesions. To mitigate against this effect, if the cutaneous burden of KS is at any time 8 or less lesions, progressive disease will require the development of at least 2 new lesions. Similarly, if the cutaneous burden of KS is at any time 8 or less nodular lesions, progressive disease will require the development of at least 2 new nodular lesions.

Stable Disease

- Any tumor measurement not meeting the criteria for Complete Response, Partial Response, or Progressive Disease.

Overall Response

- Overall response rate is the sum of complete responses, clinical complete responses, and partial responses.

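### Off-therapy criterion 3.6.1.7 delays the mandatory stop for clinically significant progression by eight weeks and does not exempt symptomatic visceral or organ- or life-threatening KS

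*Combined protocol and SAP*

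**What the plan says.** Section 3.6.1.7 has four sentences, and three of them matter here.

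- The first sets the criterion: clinically significant progressive disease, judged against the baseline for the current course, that is "sustained for eight weeks and not attributed to immune reconstitution syndrome".
- The second notes that KS can wax and wane and allows treatment through the first 6 cycles "despite meeting formal criteria for progressive disease, as long as disease progression is not clinically significant". The third requires such cases to be discussed with the Principal Investigator and the subject.
- The fourth defines the class: "Clinically significant progression includes all symptomatic visceral disease and disease which is organ- or life-threatening".

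Other off-therapy criteria in Section 3.6.1 carry no waiting period: ECOG performance status of 3 or worse (3.6.1.8), the subject's request (3.6.1.11) and the Principal Investigator's discretion (3.6.1.12). After six cycles, 3.6.1.6 ends therapy "unless continuing to derive clinical benefit, as described in Section 3.1.4". Under 3.1.6.5 the off-therapy criteria for an optional second course parallel those for the first.

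**The concern.** This is the protocol's listed stopping rule for progression, and as worded it applies the same eight-week wait to the most dangerous forms of KS as to any other clinically significant progression. The second sentence points the other way, because it withholds permission to continue in exactly those cases.

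The stake is patient safety. Section 1.2.1.3, on HIV-associated KS, says that with symptomatic visceral disease "additional systemic therapy with cytotoxic agents is indicated". Section 4.2.1 excludes other specific KS therapies from the medications allowed during protocol treatment, and 4.1.5.2 contraindicates radiation. A subject kept on pomalidomide therefore cannot also receive the treatment that the background describes as indicated, so a late stop can delay it.

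**Working it through.** The plan gives no figure to reproduce. The check is mainly textual, followed by simple arithmetic for size.

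**Step 1. Apply the first two sentences of 3.6.1.7 to each situation in cycles 1 to 6.**

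| Situation | Removal criterion (sentence 1) | Permission to continue (sentence 2) |
|---|---|---|
| Formal progression, not clinically significant | Not met at any duration | Given, after discussion |
| Clinically significant, under eight weeks | Not yet met | Withheld |
| Clinically significant, eight weeks or more, not immune reconstitution | Met | Withheld |

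The middle row is the gap: there is no mandatory stop and no permission to go on. The first row shows a second oddity. If sentence 1 reaches only clinically significant progression, sentence 2 permits something that sentence 1 never prevented. The likely intent is that dangerous progression stops therapy at once and the wait covers waxing and waning disease, but the criterion does not say so.

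**Step 2. Look for an exemption.** The fourth sentence assigns symptomatic visceral and organ- or life-threatening disease to the clinically significant class. It sets no separate timing, so these cases sit in the middle row until week eight.

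**Step 3. Compare with other sections.**

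- Section 6.2.3 counts "New visceral sites of involvement or progression of visceral disease" as progressive disease with no sustained-duration condition. For criteria measured in the clinic, progression is assigned, when feasible, "only when the criteria below have been met in two measurements spaced at least 1 week apart".
- Section 2.1.2 excludes symptomatic pulmonary KS at entry and, apart from non-ulcerating oral disease, symptomatic visceral KS. Asymptomatic visceral KS can be enrolled and could become symptomatic on study.

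**Step 4. Ceiling per course, on the literal reading and an uninterrupted schedule.** Inputs: 28-day cycles with 21 dosing days (3.1.3), and courses of 24 weeks, extendable to 48 (3.1.4).

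- 8 weeks / 4 weeks per cycle = 2 cycles.
- 2 × 21 = 42 scheduled doses.
- 8/24 = 33% of a 24-week course; 8/48 = 17% of a 48-week course.

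**Step 5. How many courses could be affected.** The documents give no rate. Section 10.4 reports 15 + 7 = 22 expansion-cohort subjects at amendment G, with up to 3 + 3 = 6 more allowed. It also anticipated 3 to 6 second courses, an estimate dated January 2013. If all of those came later, 6 + 3 = 9 to 6 + 6 = 12 courses remained to start. Assuming, without support in the documents, that 0% to 10% of courses progress in this way, the result is 0 to 12 × 0.10 = 1.2 courses. The two inputs come from different dates, and the number of the 22 still on therapy is not given, so this is only an order of magnitude.

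**The case against.** The strongest reply is that the paragraph, read as a whole, already yields the safe rule. The condition in the second sentence and the definition in the fourth do little work unless clinically significant progression is meant to stop therapy. The separate exits can be used on the day progression is found. Section 7.4.1 has the team discuss each participant weekly and the principal investigator review adverse event and response data. The comparisons in Step 3 are also not contradictions: 6.2.3 classifies response, 2.1.2 governs entry, and 1.2.1.3 is background on standard care.

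Most of this stands, and it is why the point is low in severity. It does not remove the point. The safe reading has to be inferred against the first sentence, which states the criterion. Two of the three exits depend on someone choosing to use them, and the third requires the subject to have declined to ECOG 3 or worse. A listed stopping rule should give the right trigger for organ-threatening disease without relying on those.

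A reader might infer that the protocol requires eight more weeks of pomalidomide in a subject with symptomatic visceral KS. It does not. No sentence requires dosing in that window, and the permission to continue is expressly withheld.

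**Conclusion.** The mandatory progression stop in 3.6.1.7 is worded with the wrong trigger for symptomatic visceral and organ- or life-threatening KS, and it sits awkwardly with its own second sentence. That conclusion rests on the text alone. It is a low-severity patient-safety correction.

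The 42 doses are a ceiling under a literal reading, not an expected exposure. The count of about 0 to 1 course rests on an assumed rate. Few if any subjects are likely to be affected, and the conclusion does not depend on either figure.

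The efficacy decision rules in Section 10.4 (at least 3 responders of 10, and at least 4 of 15) are unaffected. A reader might also infer that progression-free survival is biased by eight weeks. Section 10.4 times that endpoint to progression requiring a change in therapy and does not refer to 3.6.1.7. Some movement in event dates is possible, but the documents do not establish it. Progression that is not clinically significant is not at issue.

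**What to change.** Add to 3.6.1.7: *The eight-week requirement does not apply to symptomatic visceral disease or to organ- or life-threatening progression not attributed to immune reconstitution syndrome; these subjects come off therapy when the progression is documented.*

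Keep the eight-week window for other progression, such as cutaneous disease or edema, where the waxing-and-waning rationale may justify it. Make the second sentence agree with that window, since otherwise the same tension remains there. One possible wording: *Therapy may continue through the first 6 cycles despite formal progression that is not clinically significant and, for clinically significant progression outside the two exempted groups, until it has lasted eight weeks.* The sponsor should confirm that this is what the eight weeks was meant to cover.

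The cost is a wording amendment with IRB review, with no new visits, procedures or subjects. The clinical downside is that a subject whose visceral or organ-threatening progression might have reversed on drug stops earlier. The present second sentence already declines to let that subject continue.

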4 CONCOMITANT MEDICATIONS/MEASURES

4.1 CONCURRENT THERAPIES

4.1.1 Antiretroviral therapy

- 4.1.1.1 HIV infected subjects must be receiving, and adherent to, HAART.
- 4.1.1.2 Referring physicians may manage this component of care while liaising with study physician investigators, at the discretion of the Principal Investigator or Lead Associate Investigator.

4.1.1.3 Recommended combination therapy will be based on Department of Health and Human Services Guidelines for treatment of HIV infection. However, patients may have extenuating circumstances requiring deviation from these guidelines.

4.1.2 *Thromboprophylaxis*

4.1.2.1 Subjects will receive thromboprophylaxis for the duration of pomalidomide therapy (including 'rest' days), ceasing 28 days following the last cycle of pomalidomide.

4.1.2.2 Recommended thromboprophylaxis is aspirin 81mg PO once daily.

4.1.2.3 In subjects intolerant of the above, an appropriate alternate regimen may be used. Alternatives include but are not limited to enoxaparin 0.5mg/kg to a maximum of 40mg SC once daily Enoxaparin dose may be rounded to accommodate available commercial prefilled syringes with. Enoxaparin may also be considered in subjects with additional thrombotic risk factors, such as immobility or significant KS-associated edema. Patients receiving therapeutic anticoagulation for another indication (for example atrial fibrillation), whether with warfarin, enoxaparin, or another agent, may continue that agent in lieu of thromboprophylaxis.

4.1.2.4 Neither aspirin nor low molecular weight heparin will be administered when platelet count <50,000 cells/mm³.

4.1.3 *Pneumocystis jiroveci (PCP) prophylaxis*

4.1.3.1 *Pneumocystis jiroveci* prophylaxis is indicated if the CD4 count is ≤ 200 cells/ μ L and for patients with a history of PCP infection.

4.1.3.2 Recommended therapy is trimethoprim/sulfamethoxazole DS PO three times weekly.

4.1.3.3 In patients intolerant of the above, an appropriate alternate regimen may be used. Alternatives include but are not limited to dapsone 50–100 mg PO daily or 100 mg PO twice weekly; atovaquone 1500 mg PO daily; aerosolized pentamidine monthly.

4.1.4 *Mycobacterium avium complex (MAC) prophylaxis*

4.1.4.1 Consider for patients whose CD4 cells are below 50–75/mm³, and for those with historic CD4 nadir ≤ 75 /mm³.

4.1.4.2 Recommend azithromycin 1200 mg once weekly, but other agents are acceptable.

4.1.5 *Contraindicated Therapies*

4.1.5.1 Corticosteroids may be given only if the Principal Investigator or a physician Associate Investigator approves them. In general, except for physiologic replacement, corticosteroids (including topical preparations) should be avoided wherever possible, as they can have adverse effects on KS.

4.1.5.2 Radiation therapy is contraindicated for patients receiving therapy on protocol, as the effects of radiation therapy in combination with pomalidomide in patients with KS are unknown.

